6 STUDY DESIGN

6.1 Overview

This is a prospective, multicenter, single-arm, open label study designed to assess the safety and effectiveness of the Levita Magnetic Surgical System in colorectal procedures.

6.2 Sample Size and Number of Centers

The study will be conducted at up to three (3) study sites with a target maximum of 30 subjects in which the Levita Magnetic Surgical System is used for colorectal procedures.

6.3 Study Duration

Enrollment of subjects in this study is anticipated to take up to 6 months. Clinical follow-up evaluations will be conducted at discharge, and 7 and 30 days following surgery. The total study duration is expected to be approximately 7 months.

7 STUDY PROCEDURES

7.1 Subject Eligibility, Pre-Screening, and Exclusions

All subjects presenting for elective colorectal procedures are potential candidates, and will be screened for eligibility. A Screening/Enrollment Log will be provided to the study sites to maintain a cumulative tracking of all screened subjects.

Subjects must meet all study entrance criteria for enrollment in the clinical study. Reasons for screening failure(s) will be documented.

7.1.1 Inclusion Criteria

Subjects must meet ALL of the following inclusion criteria to be eligible for participation in the study:

1. Subject is at least 18 years of age
2. Subject has a BMI of at least 20 kg/m²
3. Subject is scheduled to undergo elective colorectal procedure
4. Subject, or authorized representative, signs a written Informed Consent Form (ICF) to participate in the study, prior to any study-required procedures

7.1.2 Exclusion Criteria

Subjects must be EXCLUDED from participation in this study if ANY of the following exclusion criteria are met:

1. Subject has a BMI of over 60 kg/m²
2. Emergency procedures (e.g., obstruction, severe bleeding or perforation)
3. Significant comorbidities: e.g. cardiovascular, neuromuscular, chronic obstructive pulmonary disease, and urological disease (renal failure)
4. Subjects with pacemakers, defibrillators, or other electromedical implants
5. Subjects with ferromagnetic implants
6. Clinical history of impaired coagulation confirmed by abnormal blood tests
7. Subject has an anatomical abnormality noted after initiation of index procedure that would prevent device use
8. Subject is pregnant or wishes to become pregnant during the length of study participation
9. Subject is not likely to comply with the follow-up evaluation schedule
10. Subject is participating in a clinical trial of another investigational drug or device

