2 SURGICAL SYSTEM DEVICE DESCRIPTION

The Levita Magnetic Surgical System is composed of two hand-held instruments: a Magnetic Grasper and an external Magnetic Controller.

The Magnetic Grasper (**Figure 1**) is comprised of two main components: a detachable Grasper Tip and a Shaft. Once the Magnetic Grasper is inserted and the Grasper Tip grasps the desired tissue, the detachable Grasper Tip can be detached from the Shaft and controlled externally using the Magnetic Controller. Traction of the tissue is maintained through the magnetic field attraction between the Grasper Tip and the Magnetic Controller. The Grasper Tip may be repositioned when needed using the Magnetic Grasper shaft or conventional (non-MSS) graspers. The Magnetic Grasper is compatible with a ≥ 10 mm laparoscopic port.

The Magnetic Controller (**Figure 2**) is a single unit with handles that is held external to the body and emits a magnetic field that attracts the detachable Grasper Tip. Once the Grasper Tip is attached to the desired tissue and detached from the Shaft, the Magnetic Controller is placed external to the body to magnetically attract the Grasper Tip to manipulate the target tissue. Adjusting the distance between the Magnetic Controller and the Grasper Tip will modulate the magnetic attraction used for tissue retraction/manipulation. The Magnetic Controller can then be moved freely, facilitating unrestricted shaft-less tissue retraction. If desired, the user can connect the Magnetic Controller to a

commercially available surgical support arm that is compatible with a hexagon-shaped mounting stem.

Figure 1. Magnetic Grasper

[figure not shown]
[figure not shown]

Figure 2. Magnetic Controller

The Magnetic Grasper is actuated via its handle with two distinct scissor-type motions to open and close the Jaws and to disengage the detachable Grasper Tip from the Shaft. The Magnetic Grasper can be used for retraction in the same manner as a conventional laparoscopic tissue grasper, or its Grasper Tip can be released and used with the external Magnetic Controller. When the Grasper Tip is detached from the Shaft, the Shaft can be removed and retraction of the tissue can be achieved through the magnetic attraction between the Grasper Tip and

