5 STUDY ENDPOINTS

The following endpoints will be evaluated in all enrolled subjects who undergo colorectal procedures using the Magnetic Surgical System.

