5.1 Primary Safety Endpoint

All adverse events will be captured and reported. Adverse events will be further summarized by relatedness to the MSS devices and/or procedure, seriousness, and level of severity.

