5.2 Primary Effectiveness Endpoint

Ability to adequately retract the colon and, as needed, peri-colorectal tissue and/or adjacent organs to achieve an effective exposure of the target tissue.

Adequate retraction will be deemed to be achieved if it is not necessary to use another port to insert another instrument to retract the target tissues.

Other Outcome Assessments

- Operative time
- Number of ports/incisions, and as compared to surgeon's standard of care (SOC) for this surgery type
- Time spent in the Post Anesthesia Care Unit (PACU)
- Length of stay (LOS) (time from admittance to post-anesthesia care unit until hospital discharge)
- Conversion rate (conversion to an open procedure due to inadequate MSS performance)
- Estimated blood loss
- Surgical Site Infection (SSI) rates

- Device malfunctions
- Subject satisfaction
- Investigator satisfaction with the MSS's ability to retract intended tissues and facilitate visualization of surgical site

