9 STATISTICAL SECTION

9.1 Statistical Methods

Data collected in the study will be presented using various descriptive statistics. Descriptive summaries will be the basis of study reports to generate an overall summary of the safety and effectiveness for the device.

Descriptive tables will be produced for baseline characteristics including demographics and medical history.

Missing data on study endpoints will be described.

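### Two rules can raise the descriptive effectiveness rate: anatomy-related non-use found after the operation starts leaves the denominator, and a device-related conversion to open with no added port can score as a success

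*Combined protocol and SAP*

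**What the plan says.** - **Exclusion after the start.** Section 7.1.2, item 7, and the synopsis exclude a subject if "Subject has an anatomical abnormality noted after initiation of index procedure that would prevent device use". Consent comes earlier (Section 7.2). The plan gives no objective definition of such an abnormality.
- **Who is evaluated.** Section 5 states: "The following endpoints will be evaluated in all enrolled subjects who undergo colorectal procedures using the Magnetic Surgical System". Section 6.2 sets a "target maximum of 30 subjects in which the Levita Magnetic Surgical System is used for colorectal procedures", whereas Section 9.2 speaks of enrolling 30.
- **Success.** Section 5.2 first describes the endpoint as the ability to retract well enough to give effective exposure. It then says adequate retraction is "deemed to be achieved if it is not necessary to use another port to insert another instrument to retract the target tissues". Conversion to open because of inadequate MSS performance is listed apart from this, among the other outcome assessments.
- **Analysis.** Section 9.1 is descriptive. It promises in general terms to present the data collected, and says that missing endpoint data will be described. The only tables it names are these: "Descriptive tables will be produced for baseline characteristics including demographics and medical history".
- **Safety.** Section 5.1 states: "All adverse events will be captured and reported". Section 12.1.1 requires every adverse event to be recorded whether or not it is related to the device.

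**The concern.** The main effectiveness result is a single-arm proportion in about 30 subjects. Its meaning depends on who is in the denominator and what scores as a success, and each has a gap.

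First, whether a retractor can be used at all is close to the question under study. A subject found unsuitable after the operation starts drops out of the rate, and nothing commits the report to showing how many there were. Thirty uses could come from 30 started procedures or from 35.

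Second, the deeming sentence in Section 5.2 looks only at added ports. A surgeon who gives up on the MSS and opens the abdomen may never place another port for a retractor. An attempt abandoned without a port or a conversion is not classified either, because the plan does not say whether an attempt is a use.

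Section 9.2 expects 30 subjects to give ample evidence of safe and effective use, and Section 14.11 says the study may support regulatory submissions. Readers will therefore lean on this rate.

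**Working it through.** **Inputs.** The 30 comes from Sections 6.2 and 9.2. The plan gives no expected rate, interval or threshold, so there is no figure of its own to reproduce. Two counts are assumed:
- k = procedures started in which the MSS was never used because of anatomy;
- c = uses ending in conversion to open for inadequate MSS performance, with no added port.

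No other failures are assumed.

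**Formula.** The exact (Clopper-Pearson) two-sided 95% lower limit for x successes in n is the 2.5th percentile of Beta(x, n − x + 1). When x = n this is 0.025^(1/n); for 30/30, 0.025^(1/30) = 88.4%.

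**(a) Denominator: 30 uses, all successful, plus k non-uses**

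| k | Rate among uses | Rate with non-use as failure, 30/(30 + k) |
|---|---|---|
| 0 | 30/30 = 100% (88.4%) | 30/30 = 100% (88.4%) |
| 1 | 30/30 = 100% (88.4%) | 30/31 = 96.8% (83.3%) |
| 2 | 30/30 = 100% (88.4%) | 30/32 = 93.8% (79.2%) |
| 5 | 30/30 = 100% (88.4%) | 30/35 = 85.7% (69.7%) |

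If the 30 counts started procedures instead, k = 1 gives 29/29 = 100% (88.1%) among uses against 29/30 = 96.7% (82.8%) among all started.

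**(b) Scoring: conversions within 30 uses**

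| c | Port wording read literally | Conversion as failure, (30 − c)/30 |
|---|---|---|
| 1 | 30/30 = 100% (88.4%) | 29/30 = 96.7% (82.8%) |
| 2 | 30/30 = 100% (88.4%) | 28/30 = 93.3% (77.9%) |
| 3 | 30/30 = 100% (88.4%) | 27/30 = 90.0% (73.5%) |

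**(c) Both together.** With k = 1 and c = 1: 29/31 = 93.5% (78.6%).

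**(d) One abandoned attempt among 30, no port added, the other 29 successful.**
- Not counted as use: 29/29 = 100% (88.1%).
- Counted as use, port wording: 30/30 = 100% (88.4%).
- Counted as use and as failure: 29/30 = 96.7% (82.8%).

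The text permits all three.

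**Safety text side by side.** The Section 5 lead-in, read literally, confines the safety endpoint to procedures using the MSS. Sections 5.1 and 12.1.1 cover all adverse events. The events would be recorded; what is unclear is whether subjects operated on without MSS use enter the summary.

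**The case against.** The other side has several good points.

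- **The information is largely collected.** Section 7.1 requires a cumulative log of screened subjects and documented reasons for screening failure, and Section 7.8 requires a reason for discontinuation. Section 7.4 collects conversions with reasons and a video, and Section 11.3 the device lot number for each subject. With the general promise in Section 9.1, it would be wrong to infer that non-uses go unrecorded or that nothing will be presented. What stands is narrower: no count of started procedures or post-incision non-uses is prespecified, and the plan does not say under which heading an item 7 case is recorded.
- **The endpoint's first sentence requires effective exposure.** A conversion for inadequate MSS performance contradicts that on its face, and the conversion rate is itself a listed outcome, so a reader would see c. This stands as a reason to expect sensible scoring. It does not settle the matter, because the next sentence defines adequacy by ports alone and nothing links conversion to the primary endpoint.
- **Success given use is a legitimate quantity.** Agreed. Counting anatomical non-use as failure is a different estimand, so it belongs in a supportive rate.

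Three further inferences are tempting, and the documents do not support them. Item 7 is not a route for removing failed attempts: it covers only anatomy that would prevent use. Section 2 does not make use ambiguous by saying that "The Magnetic Grasper can be used for retraction in the same manner as a conventional laparoscopic tissue grasper": conventional grasping and tip release are both use, and the gap lies between attempted and completed use. Nor does the plan say that adverse events in non-use subjects will be lost; only the Section 5 lead-in creates that tension.

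**Conclusion.** The concern holds as two separate gaps. Item 7, with Sections 5 and 6.2, takes anatomy-related non-use out of the effectiveness denominator. The deeming sentence in Section 5.2, read literally, can score a device-related conversion as a success. From an assumed 30/30, one case of either kind moves the rate by about 3 points (to 96.8% or 96.7%) and the exact lower limit by about 5 to 6 points (from 88.4% to 83.3% or 82.8%). With no such cases, nothing changes.

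These sizes rest on assumed counts and, for the first gap, on treating anatomical non-use as failure. A reader might infer that the study could wrongly declare success. The documents do not support that: there is no hypothesis test, performance goal or planned interval, so the effect is on what the reported rate means. The point is worth fixing because the scoring rule should be set before results are seen and the data are mostly collected already.

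**What to change.** 1. **Scoring (Section 5.2).** State that an abandoned attempt at MSS retraction, or conversion to open because of inadequate MSS performance, is an effectiveness failure even if no port was added. Count any attempted deployment as use.
2. **Reporting (Section 9.1).** Keep the MSS-used rate as primary. Beside it, report the number of started procedures (first incision made), every post-incision non-use with its reason, and a supportive rate among started procedures in which MSS use was intended, with anatomy-related non-use counted as failure. List non-use unrelated to device or anatomy separately, not as failure.
3. **Populations (Sections 5, 6.2, 7.1.2, 9.2).** Treat item 7 as a recorded reason for non-use; the surgeon's decision on use is unchanged. State whether the 30 counts started procedures or uses. Reconcile the Section 5 lead-in with Sections 5.1 and 12.1.1, so that adverse events are summarised in all started subjects.

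The cost is amendment wording, one case report form item (attempted, deployed or not used, with reason) and one disposition table. Reported rates may be lower. From 30/30, the supportive rate would fall by 100 − 96.8 = 3.2 points at k = 1 and 100 − 85.7 = 14.3 points at k = 5. The primary rate would fall by 100 − 96.7 = 3.3 points for one device-related conversion.

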7.2 Enrollment and Written Informed Consent

Patients who meet initial eligibility criteria will be asked to sign the Informed Consent Form before any study-specific tests or procedures are performed. The Investigator will inform the potential subject of the elements of the clinical study, including risks, potential benefits and required follow-up procedures, prior to obtaining the potential subject's informed consent.

7.3 Baseline Evaluation

The Baseline visit will occur within 30 days prior to the index procedure.

The following evaluations are required at this visit:

- Demographic Information: gender, race, age, weight, height, and smoking status
- Medical / Surgical History
- Pre-operative blood draw for determination of coagulation disorders
- Urine pregnancy test for women of childbearing potential. Note that if the screening test is more than 1 week prior to the index procedure, a second urine pregnancy test is required within 7 days of the index procedure.

7.4 Procedure

The Investigator will perform the surgical procedure in accordance with the methods detailed in the Instructions for Use (IFU).

The following intra-operative data will be collected:

- General anesthesia time
- Operative time (from the first incision to the last suture's placement)
- Device and procedure observations
- Conversion to open surgical procedure and reason for conversion
- Number of ports utilized
- Number of ports typically utilized according to surgeon's SOC for specific surgical procedure
- The need for an additional port to place another retractor to retract the colon, peri-colorectal tissues or adjacent organs
- Estimated blood loss
- Video recording of the overall procedure
- Adverse events

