1 INTRODUCTION

1.1 Background and Rationale

The Magnetic Surgical System (MSS) has been shown to retract soft tissue and organs and enable a reduction in the number of ports when used in laparoscopic procedures including cholecystectomy (Rivas et al.), bariatric surgery (Guerron et al.) and prostatectomy procedures (Diaz et al) and is cleared for commercial use (FDA clearance) for these indications in the United States. In these procedures, the MSS is used to grasp and retract soft tissues and organs so that the surgeon can visualize and access the target site of the surgery (i.e., gallbladder, liver, prostate or periprostatic tissues, respectively).

Tissue retraction is also needed in colorectal surgical procedures. This study is intended to evaluate the safety and effectiveness of the Magnetic Surgical System in colorectal procedures.

As no dedicated abdominal wall port is needed to use the MSS as a tissue retractor, a reduction in the number of ports required for the surgery, with the attendant benefits of this reduction, is anticipated.

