7.6 Follow-up

All subjects will be asked to return to the investigational site at 7 days and again at 30 days post-procedure according to the study schedule described in **Table 1**. Subjects will be queried about satisfaction with the MSS facilitated procedure at the 30 day visit and about adverse events at both study visits. Study visits should be scheduled as closely as possible to the earlier part of the visit window to allow for rescheduling if needed due to last minute schedule changes. Visits not completed within the specified visit window will be regarded as protocol deviations.

Table 1: Schedule of Assessments

Assessment	Time Frame			
	Pre-op Baseline	Index Procedure	7 day follow-up	30 day follow-up
Visit Window	- 30 days	NA	± 3 days	± 7 days
Informed Consent	√			
Medical History	√			
Demographics	√			
Blood Tests	√			
Pregnancy Test *	√	√		
Intra-operative assessments		√		
Adverse events		√	√	√
Investigator satisfaction		√		
Subject satisfaction				√

* Urine pregnancy test for all women of childbearing potential at pre-op visit and repeated within 7 days of index procedure unless pre-op visit/prior urine pregnancy test was within 7 days of index procedure.

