8 RISK / BENEFIT ANALYSIS

8.1 Benefits

Possible benefits of the Levita Magnetic Surgical System are a reduction in the number of surgical ports needed to perform the surgery, with associated reduction in post-operative pain and scarring, a shorter length of stay in the hospital, and a faster recovery.

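### The surgeon's usual port count, the only comparator for port reduction, is collected with the intra-operative data and can be stated after the ports used are known

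*Combined protocol and SAP*

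**What the plan says.** Among the Other Outcome Assessments listed after the primary endpoint in section 5.2 is "Number of ports/incisions, and as compared to" the surgeon's SOC for that type of surgery. Section 6.1 describes a "single-arm, open label study", and the protocol gives no historical or literature port count.

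Section 7.4 opens its list with "The following intra-operative data will be collected". Two consecutive items in that list supply the comparison: the number of ports used, and then "Number of ports typically utilized according to surgeon's SOC for specific surgical procedure".

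Section 7.3 introduces the baseline items with "The following evaluations are required at this visit". They are demographics, history, a blood draw for coagulation and a pregnancy test. Neither a usual nor a planned port count appears. In Table 1 (section 7.6) the row "Intra-operative assessments" is ticked in the index-procedure column only.

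The expected benefit is stated twice. Section 1.1 says that "a reduction in the number of ports required for the surgery, with the attendant benefits of this reduction, is anticipated", and section 8.1 begins its list of possible benefits with "a reduction in the number of surgical ports needed to perform the surgery".

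**The concern.** A before-and-after style comparison is only as good as its reference value. Here that value is not measured. It is what the operating surgeon says he or she usually does, and the surgeon knows which device was used and which direction of result is hoped for. If the number is given once the operation is over, it can be shaped, even without intent, by the number of ports just used. A reader of the report could not tell a reference fixed in advance from one supplied afterwards.

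What is at stake is the credibility of the benefit that the sponsor anticipates. Section 14.10 expects publication, and section 14.11 says that the study may support regulatory submissions. Once the cases are done, the timing cannot be repaired.

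**Working it through.** The plan gives no figure for port reduction and no sample-size calculation (section 9.2), so there is nothing to reproduce. The check is one of text, followed by simple arithmetic on how an error would carry through.

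**Is it the only comparator?** Yes. There is one arm (section 6.1), no external port count is given, and section 5.2 names the surgeon's SOC as the reference.

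**When is it recorded?**

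| Place | What it holds | Usual port count? |
|---|---|---|
| 7.3 Baseline | Demographics, history, blood draw, pregnancy test | No |
| 7.4 Procedure | Intra-operative list, including ports used | Yes, directly after ports used |
| 7.5 Discharge | Investigator satisfaction, stay, recovery-unit time, infection, adverse events | No |
| Table 1 | Intra-operative row ticked at the index procedure only | Not named; falls under that row |

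The section 7.4 list also contains operative time, which runs to the last suture, so the list as a whole cannot be completed until surgery ends. No section requires the usual count before incision.

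**Does another control set the timing or supply a source?**
- Section 10.1 makes the site principal investigator responsible for accuracy and completeness. It says nothing on timing.
- Sections 10.2 and 11.2 provide for consistency review, queries and full source verification. No source is defined for the usual count, so verification can confirm only that the form matches what was written down.
- The procedure video (section 7.4) can confirm ports used, but not what is usual.
- The independent physician (sections 11.1 and 13.1) adjudicates adverse events only.

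**How would an error carry through?** Let S be the true usual count, P the ports used and e the error in the stated count for a subject. The target maximum is N = 30 (section 6.2).

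- Reported mean reduction = (1/30) × Σ(S + e − P) = true mean reduction + (1/30) × Σe.
- One subject with e = +1 shifts the mean by 1/30 = 0.033 port. With e = −1 the shift is −0.033.
- For k subjects with e = +1 the shift is k/30. With assumed values k = 3, 10 and 15 it is 3/30 = 0.10, 10/30 = 0.33 and 15/30 = 0.50 port.

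The values of k and the one-port error are assumptions that show the range; the documents give neither. The formula covers all error in the stated count. Late recording would account for only some unknown part of it.

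**The case against.** The case for leaving this alone has four parts.

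- **Low weight.** The comparison is one of ten other outcomes, has no hypothesis or threshold, and is summarised descriptively under section 9.1. This stands and limits the point to a minor one.
- **Silence, not a wrong rule.** Section 7.4 lists what is collected and does not say that the usual count is entered after the ports are counted. An entry on the day of surgery but before incision would satisfy Table 1. The case report form, instructions for use and training material are not part of the documents and might fix the order. This also stands: the protocol permits late entry but does not require it.
- **Consistency checks.** A surgeon's usual count for a given procedure should be stable, so case-by-case adjustment could show up as differing values for the same surgeon and procedure. This stands in part. Such checks would miss a uniform overstatement or a procedure type seen only once, and they do not set the timing.
- **The remedy is partial.** A surgeon who signs a form in advance still knows the hoped-for direction. This stands. Early recording closes one route to bias and leaves the comparator self-reported.

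Two stronger readings are tempting, and the documents support neither. A reader might infer that surgeons will adjust the number to suit the result; the text shows only that they could. A reader might also infer that the primary effectiveness endpoint is affected. It is not: section 5.2 defines it by the need for another port for a retracting instrument and does not use the usual count.

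**Conclusion.** The point holds as a minor design weakness that is cheap to correct. The only reference for port reduction is the unblinded surgeon's own statement, and the protocol collects it at a stage where the result may already be known. Neither the primary effectiveness endpoint, the safety endpoint nor the sample size depends on it.

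The size of any bias cannot be derived from the documents. What can be said is that each subject with a usual count one port too high adds 1/30 port to the mean reduction, taking the full 30 subjects as analysed, and that a count one port too low subtracts the same. The conclusion rests on the protocol text alone; a case report form that already required the entry before incision would meet the concern in practice, though the protocol should still say so.

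**What to change.** 1. Take the usual port count out of the intra-operative list in section 7.4.
2. Before each surgeon's first study case, record that surgeon's SOC port number for each procedure type, signed and dated.
3. For each subject, record the planned procedure type before incision and report any later change, so that the reference cannot move through reclassification.
4. Report the within-subject difference (pre-recorded SOC count minus ports used) descriptively, with its distribution. State in the report that the SOC count is the surgeon's own statement.

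The cost is one form per surgeon and one pre-incision entry per subject. Sample size, endpoints and care are unchanged. The reported reduction may turn out smaller. The change does not protect against an overstatement made beforehand, which would then carry into every case of that procedure type for that surgeon. As an illustration with an assumed caseload, one surgeon with 10 of the 30 cases, all of one type and one port too high, would still add 10/30 = 0.33 port to the mean.
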